Overview and Rationale for Study. Inflammation is a primary HIV-related complication. HIV patients experience non-AIDS-related complications that are typical of older patients, such as presence of neurocognitive disorders, metabolic syndrome, bone abnormality, non-HIV-associated cancers, and neurocognitive disorders [1]. Chronic inflammation in PLWH is a significant problem that impacts the quality of life in PLWH. The effects of cannabinoids in reducing inflammation are renowned; however, the intra-cellular mechanisms and pathways that cannabinoids use to alter inflammation are yet to be discovered. Our central hypothesis is that CBD is an extremely beneficial therapeutic drug for PLWH, because it reduces inflammation by hindering pro-inflammatory monocytes via MAPK-dependent pathways. This hypothesis targets two fundamental unanswered problems in the field of HIV/AIDS, that are high HIV/AIDS NIH priorities: (i) identifying the mechanism regulating PLWH persistent inflammation, which in turn plays a pivotal role in all the main causes of death in PLWH; and (ii) investigating the role of cell-specific candidate biomarkers describing the molecular response to CBD, which may open for new cure strategies.

By mapping the effects of a controlled trial of CBD-administration at the single-cell level, we will pave the way for new candidate therapies, from CBD- and other cannabis-based therapies to the identification of novel protein targets for drug repurposing or discovery. Understanding how CBD reverses inflammation (potentially at the systemic level), will help overcome a significant challenge for HIV care and treatment, particularly for infected young adults who have a lifetime in combined antiretroviral therapy (cART). Filling this gap is particularly relevant because our findings will provide a framework for the evolving policies for clinical use of FDA-approved drugs for HIV cure strategies. As such, it has an enormous repercussion as THC is not legalized for its psychoactive properties, while CDB can be found in any grocery store in the US. Therefore, understanding CBD influence on HIV-induced inflammation is also extremely important to inform the medical community and the public answering which compound has a therapeutic validity. Our findings will potentially open a new therapeutic window for personalized and precision medicine.

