The main objective of this project will be to identify inflammatory reduction biomarkers linked to MAPK-dependent alterations after CBD administration, as well as other systemic effects on cell signaling pathways. Investigating the role of cell-specific biomarkers describing the molecular response to CBD-administration may open avenues for additional therapeutic strategies that can help reduce the burden of chronic musculoskeletal pain and other pain-related symptoms and comorbidities in people living with HIV (PLWH). The team proposes to study the effects of CBD on inflammation and chronic pain in PLWH by enrolling five persons with HIV who will provide blood samples before and after taking CBD for two months. In the process, the goal will be to establish the molecular role(s) of different immune cells using single cell RNA-sequencing. Preliminary data from this study are expected to pave the way for further investigations in larger clinical cohorts. The primary aim of this project will be to identify key inflammatory reduction biomarkers linked to MAPK-dependent alterations after CBD administration. Secondary outcomes include pain relief and reductions in pain-related symptoms. We will use a prospective pilot study design where patients will self-administer the investigational product (CBD-extract) for 60-days (2 months).

Specific Aim #1 – Determine the effects of CBD on chronic on quality of life in PLWH. We will compareQuality of Life (QoL) measures between treatment conditions, including pain and pain-related symptoms, if present.

Specific Aim #2 – Determine key biobehavioral mechanisms contributing to antiinflammatory and analgesic effects of CBD administration in PLWH. We hypothesize that change in molecular (alterations in cell signaling and reduction in inflammatory cytokines), psychological (reduction in pain-related fear and pain catastrophizing), and pain sensitivity regulation measures will be associated with pain relief, inflammation reduction, and reservoir shrinkage. We will quantify the shift in anti-inflammatory macrophage/monocyte population caused by CDB administration by examining gene expression at the single-cell level from the PBMC samples. This will allow us to accurately pinpoint gene under- or over-expression patterns at the RNA level (biomarkers), that are both induced by CBD administration in PLWH, and specific to different cells (e.g., monocytes, T cells, B cells, or other immune cells).

6. Research Plan

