CBD biomarker extraction. We will contrast clusters of the same cell type at baseline (no CBD) and their counterparts after CBD administration. The difference in gene expression, measured in fold change, p-value, and ratio of cell fraction expressing the marker gene, will determine the phenotypic effect of CBD. For each cell type, we expect to extract one or more sets of CBD-specific candidate biomarkers that together will determine a phenotypic CBD per cluster (cell type) signature.

Investigational Product & Dosing Schedule. [name] (Co-I) will oversee CBD dosage and administration.We will source the investigational product from the same batch of our hemp-extract CBD product that is being used in the original protocol under IND 147985, 'Efficacy of a controlled short-term trial of Cannabidiol (CBD) ingestion on reducing symptomatic response and facilitating recovery after induced muscle injury' (Source: SunFlora, Inc, [name])''. SunFlora is a third-party tested hemp-derived product manufacturing company. SunFlora is dedicated to producing high quality hemp-derived products formulated to be safely used by the public and are manufactured in accordance with the Food and Drug Administration (FDA) Current Good Manufacturing Practices (cGMP) for Dietary Supplements, 21 CFR Part 111. Their hemp derived products are assessed multiple times at production process control points throughout the manufacturing process. Dietary ingredients used in the manufacturing process are accompanied by certificates of analyses (CoAs) confirming their identity and specifications. All finished products are tested to ensure they meet specifications prior to being released for distribution. The label and all labeling satisfy FDA requirements found under 21 CFR 101.

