Primary Outcomes: This study takes a single-cell perspective, i.e., we will collect a large number of cells from a small number of patients, and we will measure RNA expression per single cell (not per patient). Note that from the single cell point of view, the number of patients (5-7) is sufficient to derive statistically viable results, as we will collect 5,000 cells from each patient at each time point (total 75,000-105,000 cells). Each cell will be sequence individually to read the RNA expression from a panel of approximately 20,000 genes. Cells will be pooled from all patients, and clustered via unsupervised algorithms into clusters of different cell types (e.g. T cells, B cells, monocytes). Our primary outcomes will be the extraction of gene expression patterns (RNA) from specific immune cell types found in PBMC (e.g., B cells, T cells, monocytes). We will regress these gene markers against the variation in baseline inflammation (C-reactive protein, erythrocyte sedimentation rate, and procalcitonin). After CBD administration to obtain CBD-related biomarkers for inflammation reduction. The difference in gene expression will be measured in fold change, p-value, and ratio of cell fraction expressing the marker gene. These biomarker gene will be unique for each cell type. We expect to extract specific biomarkers for each cell type and understand how CBD alters gene expressions of different immune cells in a different way-overall, we expect the genes of the MAPK signaling pathway (MAPK families play an important role in complex cellular programs like proliferation, differentiation, development, transformation, and apoptosis) to be strongly altered.

Secondary Outcomes. Self-report pain ratings will be used to determine peak pain intensity and pain persistence. The brief pain inventory (BPI) will be used to self-report pain perception. The inventory consists of rating pain on a visual analog scale (VAS). A 10cm line is drawn with 0 (no pain) on the left pole and 10 (worst pain imaginable) on the right pole. The inventory asks participants to rate their level of pain by placing a slash on the line that best represents their current level of pain as well as pain at its worst, best and average over the past 24 hours. The highest worst pain intensity reported during the intervention will be recorded as the peak pain intensity.

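### No stated outcome or analysis estimates whether CRP, ESR or procalcitonin fall during CBD use, so genes could be labelled inflammation-reduction biomarkers when mean inflammation did not fall

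*Combined protocol and SAP*

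**What the plan says.** The combined protocol and SAP gives its purpose in section 5 (Specific Aims): "The primary aim of this project will be to identify key inflammatory reduction biomarkers linked to MAPK-dependent alterations after CBD administration". Section 4 (Background) gives the central hypothesis that CBD helps people living with HIV "because it reduces inflammation by hindering pro-inflammatory monocytes via MAPK-dependent pathways".

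The outcomes and analyses are these:

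- **Primary outcome** (section 6, Primary Outcomes): "Our primary outcomes will be the extraction of gene expression patterns (RNA) from specific immune cell types found in PBMC".
- **Serum inflammation markers** (same paragraph, the only mention): "We will regress these gene markers against the variation in baseline inflammation (C-reactive protein, erythrocyte sedimentation rate, and procalcitonin". An incomplete sentence follows: "After CBD administration to obtain CBD-related biomarkers for inflammation reduction".
- **Biomarker rule** (section 6, CBD biomarker extraction): clusters of one cell type are contrasted before and after CBD, and the expression difference, "measured in fold change, p-value, and ratio of cell fraction expressing the marker gene, will determine the phenotypic effect of CBD".
- **Secondary outcomes** (section 5): "Secondary outcomes include pain relief and reductions in pain-related symptoms". Section 6 details pain ratings, PASS-20, PSQI and SF-12.
- **Aim 2** (section 5): the hypothesised molecular changes are "alterations in cell signaling and reduction in inflammatory cytokines". It also plans to quantify a shift in the anti-inflammatory monocyte/macrophage population from single-cell expression.
- **Visit schedule** (section 6, Experimental Procedures): a blood draw at each of three visits, with none of the three serum assays listed.

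**The concern.** The hypothesis is a chain: CBD lowers inflammation, it does so through monocytes, and MAPK-related expression marks the process. The plan measures the later links in detail and leaves the first unestimated. A gene whose expression changes on CBD, or correlates with a serum marker, could be reported as a biomarker of inflammation reduction in a group whose inflammation did not go down on average.

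A flat average is a realistic possibility. Eligibility in section 6 sets no minimum CRP, ESR or procalcitonin and excludes many inflammatory conditions, so there may be little room to fall. Section 5 expects these data to lead to larger cohorts, which would inherit a premise the pilot could have examined on blood it already draws.

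**Working it through.** **1. The plan's own size figure.** Patients × 3 time points × 5,000 cells: 5 × 3 × 5,000 = 75,000 and 7 × 3 × 5,000 = 105,000. Both match section 6. For a serum marker, however, the sample is 5 to 7 patients with three values each. No alpha, effect size or SD is stated for it.

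**2. Does any analysis need inflammation to fall?**

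| Element | Inflammation measure used | Estimates or requires a fall? |
|---|---|---|
| Biomarker extraction rule | None | No |
| Regression, literal reading | Baseline CRP, ESR, procalcitonin | No; no on-CBD value enters |
| Regression, read as change on change | Change in the three markers | No; see step 3 |
| Aim 2 cytokine reduction | No assay named | No test given |
| Aim 2 monocyte/macrophage shift | Transcriptomic proxy | No test, criterion or link to the serum markers |
| Secondary outcomes | None | No |

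**3. The change-on-change reading.** Let x be a patient's change in the log marker and y the change in expression. With an intercept, slope = Σ(x − x̄)(y − ȳ) / Σ(x − x̄)². Adding a constant c to every x adds c to x̄, so each x − x̄, and hence the slope and correlation, is unchanged.

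- Simulated six-patient illustration, adding −0.7, 0 or +0.7 to every log CRP change: slope 1.92 and r 0.98 in all three cases. The mean log changes are −0.83, −0.13 and +0.57, which are exp(−0.83) − 1 = −56%, exp(−0.13) − 1 = −12% and exp(0.57) − 1 = +77%.
- Simulated rejection rates (assumed two-sided 0.05) were identical for mean marker changes of −1, 0 and +1 SD. At n = 5 they were 0.048 for true correlation 0 and 0.662 for 0.9. At n = 7 they were 0.048 and 0.902.

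**4. Limit of step 3.** The property belongs to that model. In a simulation of 6 patients × 3 visits that related levels within patient, the same three shifts gave slopes of 0.67, 0.48 and −0.33, while the change-on-change slope stayed at 0.64. A model on levels can therefore react to direction. It still does not estimate the fall or require one.

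**5. Precision of the missing estimate.** Take the mean of the two on-CBD log values minus baseline. Assume a within-person SD s of log CRP of 0.3 to 0.6 (not in the documents), independent values, and the same true change in every patient. The SD of the change is s√(1 + 1/2), and the CI half-width is t(0.975, n − 1) × s√1.5 / √n.

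| n | s | Half-width (log) | Ratio × and ÷ |
|---|---|---|---|
| 5 | 0.3 | 2.776 × 0.367 / 2.236 = 0.46 | 1.6 |
| 5 | 0.6 | 2.776 × 0.735 / 2.236 = 0.91 | 2.5 |
| 7 | 0.3 | 2.447 × 0.367 / 2.646 = 0.34 | 1.4 |
| 7 | 0.6 | 2.447 × 0.735 / 2.646 = 0.68 | 2.0 |

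An observed fall just clears no change at 1 − exp(−0.34) = 29% in the best case and 1 − exp(−0.91) = 60% in the worst. A true fall of that size would be detected only about 54% to 56% of the time. For 80% power the standardised change must be 1.27 SD (n = 7) or 1.68 SD (n = 5). On the log scale that is 1.27 × 0.367 = 0.47 at best and 1.68 × 0.735 = 1.23 at worst, or falls of about 37% to 71%.

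**The case against.** The strongest defence is that this is a small mechanistic pilot. Section 4 makes attenuating inflammation a long-term goal and this study a first step. It also describes its target as biomarkers associated with inflammation reduction, and a gene that separates patients whose markers fell from those whose markers rose fits that description even at zero mean change. Aim 2 does look at inflammatory state at the cell level, where the hypothesis sits. With 5 to 7 patients, a significance test of the fall would be too demanding a gate.

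Much of this stands, and it rules out several stronger readings that a reader might infer:

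- *That the regression returns the same genes whatever inflammation does.* The model is not specified, and the invariance holds for only one form of it.
- *That the plan ignores inflammation altogether.* It names three serum markers and a monocyte/macrophage shift.
- *That follow-up assays will not be done.* The schedule does not list them, but it does not exclude them either.
- *That the label must wait for a statistically significant mean fall.* At this sample size that would often fail for lack of precision. A mean fall also would not show that any particular gene tracks it.

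The central gap remains. Explaining how a reduction comes about requires showing whether one occurred, and nothing in the documents commits the team to reporting that.

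**Conclusion.** The point holds in this limited form. The primary aim concerns biomarkers of inflammation reduction, but no stated outcome or analysis estimates change in CRP, ESR or procalcitonin, and no rule ties the label to an observed decrease. Genes could be so labelled when mean inflammation was flat or higher. Flat here means flat on average: if no patient's marker changed at all, a change-on-change regression could not be fitted, although the expression contrast would still run.

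The conclusion about the plan rests on its text. Only the precision figures rest on the assumed SD, and differences in response between patients would widen those intervals. The added estimate would be descriptive. The study is single-arm, so a reader should not take even a clear fall as an effect of CBD. Nor does the gap suggest that CBD fails to lower inflammation; the plan as written simply would not show it either way.

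**What to change.** 1. In section 6, Experimental Procedures and Primary Outcomes, list CRP, ESR and procalcitonin at visits 1, 2 and 3, on the blood already drawn.
2. Name within-patient change in one pre-chosen marker as a descriptive outcome, for example log CRP as the mean of months 1 and 2 against baseline. Treat the other two markers as supportive.
3. Report geometric mean ratios with 95% CIs and individual patient lines, with no significance gate.
4. Complete the unfinished sentence after the regression, stating the model and which marker values enter it.
5. Reserve the term inflammation-reduction biomarker for genes whose within-patient change tracks an observed decrease in the pre-chosen marker, and print that marker's mean change and CI beside the label. Otherwise describe the genes as expression changes during CBD use, associated with marker change where shown.
6. State that, without a control group, neither a fall nor an expression change can be attributed to CBD.

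The cost is one table, one wording rule and, if only baseline assays were planned, a modest laboratory charge for two further visits. The intervals will be wide, and some results will earn a less favourable label.

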Although cART suppresses the viral load, it does not eradicate HIV infection, which remains associated with relatively high levels of inflammation that may increase the risk for a range of health problems. Our preliminary data indicates that PLWH who use cannabis on a recreational level show a decrease in chronic inflammation, possibly MAPK-signaling mediated. We hypothesize that CBD is able to reduce inflammation via MAPK-dependent alterations of the circulating monocyte population.

Cannabis sativa (marijuana) and its cannabinoid derivatives, Δ 9-tetrahydrocannabinol (THC) and CBD, are largely used by people living with HIV (PLWH) to stimulate appetite, prevent weight loss (FDA approved Marinol or Dronabinol), or manage chronic pain. CBD is sold in grocery stores in the US. Although beneficial effects of cannabis on inflammation are well known, [2] and despite its widespread use, the differential impact of cannabinoids on health outcomes in PLWH remains understudied.[3] As a consequence, the cannabinoids molecular chain leading to inflammation reduction remains to be unveiled.

Cannabinoids bind to endocannabinoid system receptors CB1R, which is mostly found in the central nervous system, and CB2R, mostly found in your peripheral nervous system, especially immune cells. THC binds to CB1R and CB2R, found on the surface of immune cells and tissues, including T-cells, macrophages/monocytes, and microglia. It is known that monocyte cells treated during differentiation with THC displayed reduced expression of CD14, CD16, and CD163, therefore suggesting a fundamental alteration in phenotype [4]. Our preliminary microarray transcriptome study evidenced that peripheral blood mononuclear cells (PBMCs), obtained from patients using marijuana recreationally, show MAPK-signaling pathway alterations [4]. Based on these results, the long-term goals of this research are to determine whether it is possible to attenuate and possibly resolve chronic inflammation in PLWH with CBD. As a first step, this proposed research will determine cell-type specific CBD mechanisms altering HIV-1 infected cell state at the RNA level, and how these gene expression pattern shifts influence HIV-associated

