Study Population. Our clinical population will be men and women (N=5 to 7) 21-60 years old who are currently living with HIV (under antiretroviral therapy for 5+ years with a suppressed viral load).

Recruitment strategy. Co-I [name] has extensive experience in HIV patient recruitment and will oversee the recruitment team, during the recruitment phase, as well as the safety monitoring. Five PLWH (men and women) will be primarily recruited from The SHARC Registry (IRB# 201400073), a UF-IRB-approved registry of over 600 HIV patients who have agreed to be contacted about future research. Written informed consent will be obtained, and blood will be collected at the UF CTRB clinical research center. Inclusion criteria are: ability to read English and provide written consent; willingness to take CBD and to participate in follow up for two months; older than 21 and younger than 60; under antiretroviral therapy for 5+ years and suppressed viral load (CD4 count <350cells/ml); patients must agree to practice acceptable methods of birth control, namely sterilization (female tubal ligation or occlusion, male vasectomy), long-acting reversible contraceptives (intrauterine devices, hormonal implants), short-acting hormonal methods (pill, mini pills, patch, shot, vaginal ring), and condoms.

The main exclusion criterion will be conditions/medications that may impair the immune response (e.g. rheumatoid arthritis, cancer, diabetes chronic infections, CAD, cellulitis, autoimmune diseases such as lupus, sarcoidosis, and all medications they may affect inflammation such as aspirin, steroids, statins);), pregnancy, and current marijuana or CBD use (urine drug screen). Further exclusion criteria will be: excluding subjects taking anti-seizure medicines, with any history of seizure disorder or head trauma, any history of hepatic/liver disease or renal disease, any history of cardiovascular diseases; women who are lactating (in addition to existing exclusion criteria for pregnancy). Co-I [name] (a physician) will review conditions/medications after the initial interview before the patient is enrolled to exclude risks of drug interactions or hepatotoxicity. UF/Shands staff and students will not be considered for enrollment. Presence of chronic pain will not be considered as a necessary condition for enrollment.

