Motivation to study single cells. The molecular and cellular changes underlying the inflammation mitigation caused by CBD-administration are largely unknown, and stand as a major challenge both for understanding its basic biology (e.g., pathways involved, molecular mechanisms) and for the urgent unmet need of reducing the long-term harm chronic inflammation causes in PLWH. Our hypothesis is that CBD alters monocyte migration capacity with MAPK-dependent alterations. We expect this alteration to have

chain-effects based on cellular cross-talk, i.e., that different PBMC cell types (such as Tcells and B-cells) might express specific CBD-induced phenotypes. We hypothesize CBD-alterations to reverberate along the whole immune-modulation system through cellular cross-talk. Given the complexity of the immune response, we deem traditional (bulk) RNA sequencing as insufficient for the task. Population-averaged genomic profiling cannot adequately unravel the inter-cellular regulation in situ. This study will leverage the efficiency of newly available single-cell technologies to create a powerful dataset unveiling the functional properties of thousands of individual cells.

Sample collection and processing. We plan to collect samples from five to seven patients over three time points: baseline (no CBD), and after one and two months of CBD-administration with 5,000 cells sequenced per sample. Five to seven patients (15 to 21 samples) will provide the transcriptomes of 75,000-105,000 single cells, a large dataset for scRNAseq. Immediately after collection, samples will be collected by TBD Lab technician to be processed for scRNAseq at UF ICBR (PBMC scRNAseq experiments are routinely run at ICBR).

Data analysis. During the post-processing period, single-cell reads (count matrices) will be filtered for quality control. Unsupervised clustering will isolate statistically robust populations of similar cells. Clusters will be visualized using Principal Component Analysis (PCA), t-Distributed Stochastic Neighbor Embedding (tSNE), and Uniform Manifold Approximation and Projection (UMAP). The most informative gene expression markers will be identified by a host of non-parametric tests (e.g., the Kolmogorov–Smirnov test), comparing a given cluster against either a nearby cluster or all other clusters. Clusters of cells will be annotated by using their marker genes/pathways⁻ and prior biological knowledge to characterize each sample's cell composition.

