Safety Monitoring and Stopping Criteria: Safety monitoring will occur during the initial baseline visit as well as throughout the participant's duration in the study, including a 1week follow-up contact after study termination. As noted below, the baseline assessment conducted during the first visit will include a brief physical exam (including vital signs) and a thorough medical and psychiatric history, including a review of past medical history, concomitant medications, inclusion/exclusion criteria, and potential contraindications. Safety monitoring will include active and passive surveillance procedures using preexisting safety monitoring guidelines. Participants will be assessed actively at each laboratory visit by study personnel using the side effects/adverse events checklist. Each participant will be read each side effect/adverse event from the checklist and instructed to self-report as yes (go) or no (no go). If a participant experiences any of the side effects/adverse events from the checklist provided at the baseline visit, study personnel will then contact the study physician ([name]) for consultation. The side effects/adverse events will be triaged as mild, moderate or severe, and a determination will be made by the study physician as to whether the side effect/adverse event is due to the investigational test article or some other circumstance (e.g. food poisoning). If the reaction or event is determined to be due to the investigational test article and graded moderate to severe by the study physician, the participant will then be instructed to stop participation and advised to seek medical care by their primary physician or hospital. (Refer to stopping

criteria below). Any serious adverse reaction or event will be followed until full resolution. All adverse reactions and events will be reported to the UF IRB within 24-48-hrs and documented in the participant's file (redcap). The PI/physician decides that the participant should be withdrawn for **safety reasons** (presence of active lesions in the oral cavity/sublingual region or suffering side effects or adverse events associated with the use of the investigational product). List of side effects and adverse reactions are listed below*

Stopping Criteria:

- 1. Participant is unwilling to continue in the study.
- 2. Lack of compliance with protocol.
- 3. Investigator or study sponsor stops the study for any reason.

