Screening: Study coordinator will screen candidate to determine if they meet the inclusion criteria for the study. The baseline visit activity will be described to the patient. The patient will sign the consent form. Instruction/demonstration about CBD and dropper use will be provided.

Visit 1: Baseline Evaluation before CBD administration

Activities during visit 1:

- Patient reads and signs the consent form.
- Patient completes a brief form providing information (e.g. age, address, phone number, etc., health history).
- Measure of patient's height, weight, and vital signs (HR, blood pressure, body temperature).
- Patient completes a urine drug test
- Patient completes a urine pregnancy test is they have the ability to become pregnant
- Patient fills questionnaires: PASS (Pain Anxiety Symptom Scale; four dimensions of pain measured: cognitive anxiety, escape/avoidance, fearful appraisal, physiological anxiety), VAS (Pain Experience Visual Analogue Scales; anxiety, depression, anger), PSQI (Pittsburg Sleep Quality Index; self-report used to assess a subject's usual quality of sleep)
- A trained nurse or technician draws a blood sample
- The patient is given 2 30mL bottles with a syringe dropper with instructions/demonstration to take the solution under the tongue (0.5 cc ~1/2 dropper) twice per day (BID), 12 hours apart (morning and evening), at the prescribed daily dosage (62.5mg/day).
- The patient schedules the next test visits to the laboratory.
- The patient receives \$100 for completing this visit.

Visit 2: Follow-up after a month period of CBD administration

Activities during visit 2 (day 26-34):

- Measure vital signs of the patient as in visit 1.
- Questionnaire filling as in visit 1.
- Blood draw as in visit 1.
- The patient schedules the next test visits to the laboratory.
- The patient receives \$100 for completing this visit.

Visit 3: Follow-up after a two-month period of CBD administration

Activities during visit 3 (day 56-64):

- Measure vital signs of the patient as in visit 1.
- Questionnaire filling as in visit 1.
- Blood draw as in visit 1.
- The patient schedules the next test visits to the laboratory.
- The patient receives \$100 for completing this visit.

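### The inclusion criteria attach a CD4 count to viral suppression, so suppression is left undefined and the role of the CD4 limit is unclear

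*Combined protocol and SAP*

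**What the plan says.** Section 6, Study Population, describes men and women "who are currently living with HIV (under antiretroviral therapy for 5+ years with a suppressed viral load"). It gives no value for suppression and does not mention CD4. The operative list under Recruitment strategy asks for candidates "under antiretroviral therapy for 5+ years and suppressed viral load (CD4 count <350cells/ml"). That bracket contains the only number attached to suppression.

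Section 4 (Background) explains why suppression matters: "Although cART suppresses the viral load, it does not eradicate HIV infection, which remains associated with relatively high levels of inflammation".

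Eligibility is checked in several places. Under Experimental Procedures, Screening, "Study coordinator will screen candidate to determine if they meet the inclusion criteria for the study". The baseline assessment under Safety Monitoring and Stopping Criteria includes "a review of past medical history, concomitant medications, inclusion/exclusion criteria, and potential contraindications". Under Recruitment strategy, a co-investigator "has extensive experience in HIV patient recruitment and will oversee the recruitment team", and a physician co-investigator reviews conditions and medications before enrolment, looking for interaction and liver-toxicity risks.

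**The concern.** Viral load and CD4 count are different quantities, and no conversion turns one into the other. The protocol requires the first and supplies a number only for the second. A coordinator holding a candidate's records cannot tell from this sentence whether CD4 stands in for suppression, is a further requirement, or is a slip.

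At stake is the definition of the study population. The rationale concerns inflammation that persists although therapy controls the virus, so suppression is what makes a candidate relevant to the question. T cells are also among the cell types to be analysed, so a reader of the results needs to know whether participants were selected for a low CD4 count. With only five to seven participants planned, the report should be able to say exactly whom it describes.

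**Working it through.** No sample-size or power figure is involved. The check sets the relevant places side by side.

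**1. Every mention of viral load.** There are three: one in Background and two in section 6 (Study Population and the inclusion list). None carries an HIV-RNA value, an assay limit or a look-back window. CD4 appears only in the inclusion list. Elsewhere, RNA refers to gene expression or sequencing.

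**2. Who is eligible under each reading.** All candidates are taken to meet the other criteria. 'Below' and 'at or above' refer to the bracketed CD4 figure in whatever unit was intended.

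| Candidate | (a) Bracket defines suppression | (b) Bracket is a separate condition | (c) Study Population paragraph alone |
|---|---|---|---|
| Suppressed, CD4 below | eligible | eligible | eligible |
| Suppressed, CD4 at or above | not eligible | not eligible | eligible |
| Not suppressed, CD4 below | eligible | not eligible | not eligible |
| Not suppressed, CD4 at or above | not eligible | not eligible | not eligible |

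The readings disagree in two of the four rows. Reading (a) uses the wrong quantity and could admit people without suppression. Reading (b) excludes suppressed people with higher counts, for no stated reason. Under (b) and (c), 'suppressed' still has no value, so even the row labels cannot be applied consistently.

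**3. Whether another section settles it.**
- Screening refers back to the inclusion criteria and names no laboratory test or record.
- The baseline assessment consists of examination, vital signs, history and a review of the same criteria.
- The physician's pre-enrolment review covers conditions and medications, and viral load is not mentioned.
- At Visit 1, "A trained nurse or technician draws a blood sample", with no assay named. Under Sample collection and processing, "samples will be collected by TBD Lab technician to be processed for scRNAseq at UF ICBR". Primary Outcomes adds procalcitonin, erythrocyte sedimentation rate and C-reactive protein. Aim 2 adds inflammatory cytokines and a hypothesis about the viral reservoir. None of these is a viral-load eligibility test.
- The recruitment registry of over 600 patients and the medical history could hold viral-load results, but neither is designated for that purpose.

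Every check therefore returns to the same sentence.

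**4. The printed unit.** 350 cells/ml ÷ 1,000 = 0.35 cells per microlitre. This is noted only because the unit needs confirming; steps 1 to 3 do not depend on it.

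**The case against.** The strongest reply is that HIV clinicians know what suppression means, the recruitment team is experienced, and recent viral-load results may well be in patients' records. That is plausible, and it limits the practical harm. It does not repair the text. The protocol attached a number to the term, and it is a number of the wrong kind, so staff must either apply it or disregard a written criterion.

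A second reply is that a summary paragraph need not repeat every criterion. That stands. A reader might infer that Study Population and the inclusion list contradict each other, but the documents show only that a restriction appears in one place without explanation.

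A third concerns the visit schedule. A reader might infer from the absence of HIV-RNA and CD4 tests in the visit lists that neither will be done. The lists do not support that. They name no blood assay at all, not even those planned elsewhere in the protocol. What is missing is a named source for verifying suppression.

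Finally, a reader might infer from the printed unit that almost nobody could qualify. The unit may be an artefact of converting the PDF to text, and staff would be unlikely to apply it literally. Nothing here should rest on it.

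**Conclusion.** The point holds. As written, the inclusion criterion does not define suppression, and the role of the CD4 figure cannot be determined from the text. This is a defect in a written criterion for the population-defining characteristic, and it should be corrected before enrolment.

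Its size cannot be expressed as a number of candidates: the documents give no CD4 distribution and no share of registry members who are suppressed. A reader might go further and infer a biased primary outcome or a recruitment failure. The documents support neither. The planned contrast is between cells before and after CBD, and nothing shows how an unclear entry rule would push that contrast in one direction. The demonstrated consequence is uncertainty about who is eligible and whom the results describe.

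The conclusion assumes that the inclusion sentence was read correctly from the PDF apart from, possibly, its unit, and that the opening material, which was not available, contains no HIV-RNA criterion.

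**What to change.** Before enrolment, the sponsor should say what the bracket was meant to do and reconcile it with both the suppression requirement and the Study Population paragraph. Then:

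- State suppression as an HIV-RNA criterion, with the value and look-back window set by the study physician.
- In the Screening paragraph, name the record or other source from which suppression is verified.
- If a CD4 limit is intended, list it as its own criterion, with direction, unit and reason confirmed by the sponsor, and carry it into the Study Population paragraph. If it is not intended, the bracket should go.

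No value is proposed here for either quantity. The cost is a short amendment to the inclusion sentence and the Screening paragraph, and to Study Population if a CD4 limit is kept. Candidates without a recent viral-load record would need one before eligibility can be confirmed; the documents do not say how many that would be.
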